## 6.1.4 Description of other efficacy variables

| Variable (CRF annotation)   | How to be presented  |
|---|--|
| Subject completed global and pain VAS (PGPVAS)                                      | # patients and % /category, by visit
(2 categories: Yes/No) |
| Global and Pain VAS Date (PGPDT)  | Listing only   |
| Patient Assessment of Pain Today, cm (PAP)  | n, mean (95% CI), sd, median, min, max,
by visit            |
| Patient Global Assessment of Disease Activity
Today VAS, cm (PGADA, dataset VAS) | n, mean (95% CI), sd, median, min, max,
by visit            |

Study SynAct-CS002 – Statistical Analysis Plan

| Investigator completed Investigator Global VAS
(IGVAS)   | <pre># patients and % /category, by visit (2 categories: Yes/No)</pre>                                |
|---|---|
| Investigator Global VAS Date (IGVASDT)  | Listing only  |
| Investigator Global Assessment of Disease
Activity Today VAS, cm (IGADA, dataset VAS)            | n, mean (95% CI), sd, median, min, max,
by visit   |
| C-Reactive Protein (CRP), mg/L (derived from CRP and CRP_U, see Section 7.9.2)                      | n, mean, sd, median, min, max, by visit   |
| C-Reactive Protein (CRP), Out of range and
Clinically significantly abnormal (CRP_OR,
CRP_CS) | <pre># patients and % /category (1 category CRP_OR; Yes, 2 categories CRP_CS; Yes/No), by visit</pre> |

### 6.2 Exploratory Analysis

Variables are listed below (CRF annotation presented in parenthesis), along with a short description of how they will be presented.

For a list of proposed tables, see Appendix 4.

| Variable (CRF annotation)               | How to be presented |
|---|---------------------|
| Plasma concentrations of AP1189 (ng/mL) | Listing only        |

## 7 SAFETY AND TOLERABILITY ANALYSES

All safety parameters (vital signs, ECG, AEs/SAEs, laboratory abnormalities, etc.) will be summarized by treatment as well as for all subjects in total, by time point. Individual subject listings will also be prepared for all safety variables. Listings will include flagging of clinically notable vital sign abnormalities, as defined in protocol Table 5.

Patients with no post randomization data who cannot be contacted will not be counted in frequency tables. If included, such patients would reduce the frequency of Adverse Events.

Patients will be tabulated according to treatment received. Patients who have not received any trial medication (neither active treatment nor placebo) will not be included in frequency tables.

Variables are listed below (CRF annotation presented in parenthesis), along with a short description of how they will be presented.

For a list of proposed tables, see Appendix 4.

Study SynAct-CS002 – Statistical Analysis Plan

## 7.1 Medical history variables

| Variable (CRF annotation)                                    | How to be presented                      |
|--|--|
| Any relevant medical and/or surgical history                 | # patients and % /category               |
| (MHYN)   | (2 categories: Yes/no)                   |
| Medical diagnosis/surgical procedure                         | # patients and % per diagnosis/procedure |
| (MHTERM, MHONG)  | (unknown no. of categories)              |
| Medical diagnosis/surgical procedure start date
(MHSTDAT) | Listings only                            |

## 7.2 Prior and concomitant medication variables

| Variable (CRF annotation)  | How to be presented  |
|--|--|
| Any concomitant medications (screening) or changes since last visit (CMYN) | # patients and % /category
(2 categories: Yes/No), by visit |
| Reported generic name of medication (CMTRT)                                | Listing only   |
| Total daily dose (CMDOSE)  | Listing only   |
| Unit (CMDOSU)  | Listing only   |
| Route of administration (CMROUTE)  | Listing only   |
| Frequency (CMDOSFRQ)   | Listing only   |
| Start date (CMSTDC)  | Listing only   |
| Stop date (CMENDC)   | Listing only   |
| Ongoing (CMONG)  | Listing only   |
| Indication (CMIND)   | Listing only   |
| AE no, if given to AE (CMAENO)   | Listing only   |

## 7.3 Pregnancy test

| Pregnancy test taken (PTYN, PTREAS, UPTYN, UPTREAS) | # patients and % /category, by visit
(2 categories: Yes/no)                    |
|---|---|
| Date of pregnancy test (PTDAT, UPTDAT)              | Listing only  |
| Result of pregnancy test (PTRES, UPTRES)            | <pre># patients and % /category, by visit (2 categories: Negative/Positive)</pre> |

## 7.4 Physical Examination

| Physical examination performed (PEYN)   | # patients and % /category, by visit
(2 categories: Yes/no)   |
|---|--|
| Date of physical exam (PEDT)  | Listing only   |
| General appearance, normal/abnormal,
clinically significant (GENAPP, GENAPP_DES,
GENAPP_CS) | # patients and % /category, by visit
(3 categories for GENAPP:
Normal/Abnormal/Not Done, plus any
description if abnormal; 2 categories for
GENAPP_CS: Yes/no) |
| Dermatological, normal/abnormal, clinically significant (SKIN, SKIN_DES, SKIN_CS)                 | # patients and % /category, by visit
(3 categories for SKIN: Normal/Abnormal/Not
Done, plus any description if abnormal; 2
categories for SKIN_CS: Yes/no)        |
| Thyroid, normal/abnormal, clinically significant
(THYR, THYR_DES, THYR_CS)                     | # patients and % /category, by visit
(3 categories for THYR: Normal/Abnormal/Not
Done, plus any description if abnormal; 2
categories for THYR_CS: Yes/no)        |
| Head, neck, throat, normal/abnormal, clinically significant (HNT, HNT_DES, HNT_CS)                | # patients and % /category, by visit
(3 categories for HNT: Normal/Abnormal/Not
Done, plus any description if abnormal; 2
categories for HNT_CS: Yes/no)          |
| Heart / Lungs, normal/abnormal, clinically significant (RESP, RESP_DES, RESP_CS)                  | # patients and % /category, by visit
(3 categories for RESP: Normal/Abnormal/Not
Done, plus any description if abnormal; 2
categories for RESP_CS: Yes/no)        |

Study SynAct-CS002 – Statistical Analysis Plan

| Abdomen, normal/abnormal, clinically
significant (ABDOM, AB_DES, AB_CS)               | # patients and % /category, by visit
(3 categories for ABDOM:
Normal/Abnormal/Not Done, plus any
description if abnormal; 2 categories for
ABDOM_CS: Yes/no) |
|--|--|
| Lymph nodes, normal/abnormal, clinically significant (LYMPH, LYMP_DES, LYMP_CS)          | # patients and % /category, by visit
(3 categories for LYMPH: Normal/Abnormal/Not
Done, plus any description if abnormal; 2
categories for LYMP_CS: Yes/no)     |
| Musculoskeletal, normal/abnormal, clinically
significant (MUSKU, MUSKU_DES, MUSCU_CS) | # patients and % /category, by visit
(3 categories for MUSKU:
Normal/Abnormal/Not Done, plus any
description if abnormal; 2 categories for
MUSCU_CS: Yes/no) |
| Cardiovascular, normal/abnormal, clinically significant (HEART, HEART_DES, HEART_CS)     | # patients and % /category, by visit
(3 categories for HEART: Normal/Abnormal/Not
Done, plus any description if abnormal; 2
categories for HEART_CS: Yes/no)    |
| Neurological, normal/abnormal, clinically significant (NEUR, NEUR_DES, NEUR_CS)          | # patients and % /category, by visit
(3 categories for NEUR: Normal/Abnormal/Not
Done, plus any description if abnormal; 2
categories for NEUR_CS: Yes/no)      |
| Joints, normal/abnormal, clinically significant
(JOINT, JOIN_DES, JOIN_CS)            | # patients and % /category, by visit
(3 categories for JOINT: Normal/Abnormal/Not
Done, plus any description if abnormal; 2
categories for JOIN_CS: Yes/no)     |

## 7.5 Height and Weight

| Height (HEIGHT)                            | Listing only |
|--|--------------|
| Weight (WEIGHT)                            | Listing only |
| Weight, clinically significant (WEIGHT_CS) | Listing only |

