8.4.3 MC3 Receptor (MC3R)

MC3R gene encodes a G protein-linked receptor, coupled to both cAMP - and inositol phospholipid - Ca^{2+} - mediated signaling systems. The MC3R is the only MCR activated by γ MSH with potency similar to that of other. MC3R expression occurs in brain, placenta, and gut but not in melanoma cells or in the adrenal gland MC3R expression also occurs in the heart, in human monocytes, and in mouse peritoneal macrophages. A map of MC3R expression in the brain obtained by *in situ* hybridization showed abundant presence in the hypothalamus and limbic system, but signals for this receptor were also present in the septum, thalamus, hippocampus, and midbrain MC3R appears to participate in modulation of autonomic functions, feeding, and inflammation Hypothalamus and bradycardia elicited by the release of α MSH from the arcuate neurons appear to be mediated by MC3R and MC4R located in the medullary dorsal-vagal complex Participation of MC3R in energy homeostasis was disclosed in MC3R-deficient mice, which showed increased fat mass, reduced lean mass, and higher ratio of weight gain to food intake Recent data suggest that MC3R activation mediates protective influences of MC's in myocardial ischemia/ reperfusion-induced arrhythmias in rats Furthermore, activation of MC3R has clear anti-inflammatory influences MC22.

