11.3.2 Benefits and Risks of Participation

The potential benefits of participation, for all subjects in this study, is close monitoring of their medical condition and safety. Those randomized to an active treatment may have a benefit of less pain in affected joints. Subjects randomized to placebo are not expected to obtain any additional benefit, beyond close monitoring of their medical condition and safety.

Based on available non-clinical data, AP1189 appears to be well tolerated at dose levels that induce exposure well above the expected therapeutic level expected to be reached with C_{Max} values around 175 ng/ml.

The toxicology studies showed clinical signs from the gastrointestinal system (reduced appetite, vomiting, and loose stools), the central nervous system (subdued behavior). The clinical signs were most pronounced following *iv* dosing and thereby expected to be associated with high peak concentrations that hardly will be possible to reach following oral dosing. Further, AP1189 at high dose levels induced increased liver weight in rats and minipigs increased kidney weight in minipigs and increased the weight of the ovaries in female rats. Also, hypertrophy/hyperplasia of the thyroid glands was found to be most prominent in the rats. Follow-up studies in minipigs have identified that the treatment-induced increases liver weight was fully reversible following recovery associated with a fully reversible induction of phase I and phase II enzymes. Consequently, the liver findings are to be considered related to increased workload due to fully reversible phase 1 and phase 2 enzyme induction. Likewise, the follicular thyroid hyperplasia in rats most likely is associated with increased hepatic turnover of thyroid hormones.

Protocol Code Number: SynAct-CS002

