20 SCHEDULE OF VISITS

The schedule of visits and main procedures at each visit are summarized in the study flowchart below and are identical for Part 1 and Part 2.

Table 3: Study Flow Chart

Protocol Code Number: SynAct-CS002

	1	2	3	4	5	6	7	8
Visit	Screening	Baseline						EOS Safety follow- up call ²
Week	-2	0	1	2	3	4	5	8
Visit Window	-14 to -1d	Day 0	±1d	±1d	±1d	±1d	±1d	±3d
Informed consent	Х							
Randomization		X						
Demographics	Х							
Medical and surgical history	Х							
Inclusion/Exclusion criteria	Х	Х						
Pregnancy test (serum β-HCG)	Х							
Pregnancy test (dipstick)		Х	Х	Х	Х	Х	Х	
TB test ¹	Х							
Physical examination	Х						Х	
Vital signs	Х	Х	Х	Х	Х	Х	Х	
Height and weight ³	Х	Х	Х	Х	Х	Х	Х	
Concomitant medications	Х	Х	Х	Х	Х	Х	Х	
Concomitant therapy	Х	Х	Х	Х	Х	Х	Х	
Electrocardiogram (ECG)	Х	Х	Х	Х	Х	Х	Х	
X-ray of chest, hands, and feet	Х							
SJC and TJC	Х	Х		Х		Х	Х	
CDAI	Х	Х		Х		Х	Х	
Investigator Global VAS ⁵	Х	Х		Х		Х	Х	
Patient Global VAS	Х	Х		Х		Х	Х	
Patient Pain VAS	Х	Х		Х		Х	Х	
FACIT-Fatigue		Х		Х		Х	Х	
DAS28		Х		Х		Х	Х	
HAQ-DI (Health Assessment Questionnaire-Disability Index)		Х		Х		Х	Х	
SAEs/AEs		Х	Х	Х	Х	Х	Х	Х
Blood samples (biochemistry and TSH, T3, and T4)	х	х	х	х	х	Х	х	
Blood samples (hematology)	Х	Х		Х		Х	Х	
Blood sample (MC1R genotype analysis) ⁷		х						
HBsAg, HBV antibody & HCV antibody ⁴	Х							
PK (exposure)			Х	Х	Х	Х		
C-Reactive Protein (CRP)	Х	Х		Х		Х	Х	
RF or anti-CCP	Х							
Cytokines ⁶		Х		Х		Х		
Urinalysis	Х						Х	
Dispensing of IMP		Х	Х	Х	Х			
Accountability of returned IMP			Х	Х	Х	Х		

^{1:} QFG-IT (Mantoux test can be used if QFG-IT is not possible)

Protocol Code Number: SynAct-CS002

- 2: WD: Withdrawal. In case of prematurely subject withdrawal, the final visit should occur 7 days after the last IMP. Four weeks after the last IMP the subject will have a final safety follow-up call (EOS).
- 3: Height only at screening
- 4: Hepatitis B surface antigen (HBsAg), Hepatitis B virus (HBV), Hepatitis C virus (HCV)
- 5: Visual Analog Scale (VAS)
- 6: CXCL13, IL-1 β , IL-6, IL-10, and TNF- α
- 7: At baseline or any other visit after randomization

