21.1 Safety Assessments

21.1.1 Medical History

A complete medical (and surgical) history of each subject will be collected and documented during screening to determine the subject's eligibility for the trial. The medical history will include, but may not be limited to, prior and current concomitant disease and treatments, including all previous and current therapies for RA.

Protocol Code Number: SynAct-CS002

Relevant medical history will be recorded in the eCRF and includes diagnosis and assessments of any current medical condition and concurrent health conditions.

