21.1.5 Height and Weight

Subject height will be measured at the Screening Visit, while weight will be assessed at all visits except at the visit 8 (EOS/Safety follow-up call).

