23.4 Safety Analysis

The primary safety endpoint is the safety of AP1189 against placebo by evaluating adverse events (AEs), serious adverse events (SAEs), and laboratory abnormalities. All safety parameters (ECG, vital signs, AEs/SAEs, laboratory abnormalities, etc.) will be summarized by treatment and time point.

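### Weight is a safety assessment at seven visits, but SAP 7.5 plans only a listing of it, with no declared exception to the rule that safety parameters are summarised by treatment and time point

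*SAP*

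**What the plan says.** Protocol 21.1.5 sits under the heading "21.1 Safety Assessments" and states that "weight will be assessed at all visits except at the visit 8 (EOS/Safety follow-up call" is the one exception. The flow chart in Protocol Section 20 agrees and treats height differently, with the footnote "Height only at screening".

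Protocol 23.4 sets the analysis rule: "All safety parameters (ECG, vital signs, AEs/SAEs, laboratory abnormalities, etc.) will be summarized by treatment and time point". SAP 3.1 repeats it. SAP 7 states it again, also for each time point: "All safety parameters (vital signs, ECG, AEs/SAEs, laboratory abnormalities, etc.) will be summarized by treatment as well as for all subjects in total". It then says that subject listings are prepared as well.

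SAP 7.5, inside the safety and tolerability section, has three rows: height, weight ("Weight (WEIGHT" is the row label) and a clinical-significance flag for weight, WEIGHT_CS. All three are to be listed only. SAP 5.1 summarises weight at screening as a demographic variable.

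**The concern.** A variable that the protocol collects repeatedly for safety, and for which the CRF holds an investigator's significance flag, gets no planned treatment-group summary after treatment starts. A small average change spread over many subjects is difficult to pick out of a by-subject listing. If weight moved differently on AP1189 and placebo, no table described in the SAP text would show it. The departure is also silent. A reader of the study report who relied on the general rule would expect a weight table and find no reason for its absence.

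**Working it through.** There is no published figure to reproduce here. The check is a count of visits and a comparison of the texts.

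1. **Visits at which weight is measured.** The flow chart, Protocol 21.1.5 and the visit descriptions in Protocol 20.1.1 to 20.1.7 agree on Visits 1 to 7. Visit 8 is a telephone call, so 8 − 1 = 7. Screening and baseline precede treatment, so 7 − 2 = 5 visits are post-baseline: weeks 1, 2, 3 and 4, and week 5, which is one week after the last dose.

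2. **Visits with a weight summary by treatment in the SAP text.** SAP 5.1 gives screening only. SAP 7.5 gives none. That is 1 of 7 overall and 0 of 5 after baseline. The screening value precedes treatment and cannot show a drug effect.

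3. **Is weight within the rule?** The rule names four kinds of safety data and leaves the list open. Weight is placed under safety assessments in the protocol and under safety analyses in the SAP. It also has a clinical-significance flag of the same type as those for blood pressure, heart rate and respiratory rate.

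4. **Does a listing satisfy the rule?** No. SAP 7 provides listings for all safety variables on top of the summaries.

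5. **How are the neighbouring variables treated?**
   - Vital signs (SAP 7.6), ECG intervals (SAP 7.7) and laboratory values (SAP 7.9) get descriptive statistics by visit.
   - The significance flags for vital signs and laboratory values get counts and percentages by visit.
   - Weight and WEIGHT_CS get neither.

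6. **Is the exception declared?** SAP 3.12 sets out the departures from the protocol and closes by saying that no others have been identified. Weight is not among them.

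7. **What the listing would contain.** At the planned minimum number of completers, 90 + 45 = 135 subjects, there would be 135 × 7 = 945 weights, of which 135 × 5 = 675 are post-baseline.

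**The case against.** The strongest reply is that weight is not clearly caught by the rule. It is not one of the named examples. Protocol 23.3 places it among the demographic parameters, which SAP 5.1 follows. It is not part of the primary safety endpoint, and the design-choice criteria in Protocol 15.10 do not mention it. Position under Protocol 21.1 is not decisive either: concomitant medication and X-ray sit there too, and the SAP mostly lists the first and tabulates only whether the second was taken. On this view SAP 7.5 is a specific provision that qualifies a general sentence.

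Part of this stands. Weight is peripheral to the named safety endpoint, and location alone does not settle the matter. But weight is a repeated numeric measure with a significance flag, so its natural comparators are the vital signs, not X-rays or medication names. The demographic reading does not help either, because SAP 5 says that variables measured more than once are summarised by time point, and SAP 5.1 then confines weight to screening. If SAP 7.5 is a deliberate exception, SAP 3.12 is where it should appear.

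A second reply is that the table shells in SAP Appendix 4 are a separate document that was not available. A weight table there cannot be excluded. The revision history records a plasma-concentration table in Appendix 4 although SAP 6.2 calls that variable listing-only, so the two can differ. Even then SAP 7.5 would need correcting to match.

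Two stronger readings are tempting, and the documents support neither.

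- **A drug effect on weight could not be seen.** Individual weights and the flag are listed, and a weight change reported as an adverse event would be tabulated under SAP 7.10.
- **Weight is a mechanism-related safety variable for AP1189.** The protocol does say "Participation of MC3R in energy homeostasis was disclosed in MC3R-deficient mice, which showed increased fat mass", and toxicology did show "clinical signs from the gastrointestinal system (reduced appetite, vomiting, and loose stools" among its findings. But the first comes from receptor-deficient mice. Protocol 11.3.2 says that the toxicology signs were most pronounced after intravenous dosing, at peaks that oral dosing could hardly reach. Protocol 8.4.4 attributes the food-intake effect of αMSH to MC4R, whereas Protocol 11.2 describes AP1189 as a biased agonist at MC1R and MC3R. The protocol's Phase 1 summaries report no weight signal.

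**Conclusion.** The inconsistency holds and is minor. Both documents promise a summary of every safety parameter by treatment and time point. The SAP text plans none for weight at any of the five post-baseline visits and does not declare the omission. The practical consequence is that a group-level shift would be hard to detect from the planned output. Relevance to AP1189 is plausible but not established.

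The conclusion assumes that weight counts as a safety parameter, which its place in both documents supports, and that Appendix 4 contains no weight table. It affects no efficacy result, primary safety endpoint or design criterion. No precision figure for a weight difference is offered: the documents give no standard deviation for weight change, and the safety analysis is descriptive, with no between-arm comparison planned.

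**What to change.** In SAP 7.5, replace listing-only for WEIGHT with the descriptive statistics used in SAP 7.6 (n, mean, SD, median, minimum, maximum) by visit and treatment. Present WEIGHT_CS as number and percentage of patients by visit. Height can stay as it is, because it is measured once and already summarised in SAP 5.1. Check that Appendix 4 agrees with the revised section.

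A change-from-baseline row for weight would be useful, but it is an optional addition: SAP 7.6 has no such row for vital signs, and the summary rule does not require one.

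If the sponsor prefers to keep weight as a listing, SAP 3.12 should record and justify the exception.

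The cost is one extra descriptive safety table from data already collected. No procedure, endpoint or sample size changes.

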## 7.6 Vital Signs

| Variable (CRF annotation)                        | How to be presented  |
|--|--|
| Vital signs measured (VSYN)                      | # patients and % /category
(2 categories: Yes/No), by visit         |
| Date of vital signs (VSDT)                       | Listing (and used to define visit)                                     |
| Time of vital signs (VSTM)                       | Listing only   |
| Systolic BP, mmHg (SBP)                          | n, mean, sd, median, min, max, by visit                                |
| Systolic BP, clinically significant (SBP_CS)     | <pre># patients and % /category (2 categories: Yes/No), by visit</pre> |
| Diastolic BP, mmHg (DBP)                         | n, mean, sd, median, min, max, by visit                                |
| Diastolic BP, clinically significant (DBP_CS)    | <pre># patients and % /category (2 categories: Yes/No), by visit</pre> |
| Heart rate, bpm (HR)                             | n, mean, sd, median, min, max, by visit                                |
| Heart rate, clinically significant (HR_CS)       | <pre># patients and % /category (2 categories: Yes/No), by visit</pre> |
| Respiratory rate, breaths/min (RR)               | n, mean, sd, median, min, max, by visit                                |
| Respiratory rate, clinically significant (RR_CS) | # patients and % /category
(2 categories: Yes/No), by visit         |

